8.1 GENERAL AND BASELINE CHARACTERISTICS

The numbers of patients entering the study will be recorded. Reasons for treatment and study discontinuation, withdrawal and loss to follow-up will be recorded. The date the first patient recruited and last patient completed or termination will also be noted. Protocol deviations including failure to meet inclusion and exclusion criteria will be recorded. Adverse events will also be recorded.

Serious protocol deviations defined as breach of the conditions and principles of ICH GCP or the study protocol, which is likely to effect to a significant degree the safety or physical or mental integrity of the subjects of the study, or the scientific value of the study will be recorded. Patients not withdrawn with a serious device related adverse event will be recorded as a serious protocol deviation.

In order to describe the sample and facilitate analysis of secondary objectives, the following baseline characteristics and parameters will be collated, either from the CRF or the patients' records (using EMIS patient clinical record system), see also Appendix 2:

- Patient demographics, including age and sex.
- Pre-existing co-morbidities, including peripheral arterial disease, diabetes, heart failure.
- Age of and size of foot/leg ulcer wound at baseline
- Dressing used before presentation at baseline.
- Presence or absence of infection

8.2 SAMPLE SIZE CALCULATION

The primary outcome, presence of bacterial infection is used for sample size calculation. Data from studies involving another point-of-care test (Jonker et al, 2020 and Jonker et al 2022) gives some guidance on the incidence of wound infection as defined by clinical staff. Circa 5% of samples were deemed as infected by clinical staff. A hypothetical difference in opinion/outcome of 4% is used to determine the required sample size that has sufficient power to detect such a difference.

Power calculations for sample size, 80% power and 5% significance, based on two-sided Chi-squared test. A priori power calculations using GPower 3.1 software, result in the following sample size summarized in Table 6. The raters are the WOUNDCHEK WCBC and the clinical staff. Patients will be recruited from the adult (age 18+) population routinely seen by the evaluating clinical staff members. Attrition rate — determined in other similar studies — is anticipated to be 10%.

Table 6, Sample size calculation for BIOME study

	No infection	Infection		
Rater A (hypothetical)	0.95	0.05		
Rater B (hypothetical)	0.91	0.09		
	Power beta of 80%, Alpha p-value o size 0.184	ample size required without any attrition: 234 samples. Emple size required with 10% attrition: 258 samples		
	week 0 and week 6 (258 sar attend twice, eg due to a we			

The above sample size will also allow to assess the secondary objective, ie concordance between the two raters – namely clinical opinion and WOUNDCHEK™ test result - at a confidence level of 90% and Kappa concordance level of 0.80 (calculated via https://wnarifin.github.io/ssc/sskappa.html).

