	Evaluate if there are factors associated with infection rates and/or WOUNDCHEK™ result, including clinical indicators of infection such as erythema, purulence, odour, and patient characteristics (health status, co-morbidities, demographic).
	Assess if there are any trends in bacterial protease detection rates in ulcers when patients are followed up, ie result of first test versus second follow-up test of same ulcer
	Evaluate if clinical staff deviate from their initial treatment plan once the WOUNDCHEK result is available to them during a consultation

	T
Inclusion & Exclusion	Inclusion criteria:
criteria	- Adult patients aged ≥ 18 years
	- Patients can be newly presenting to or existing users of the
	specialist service in question (eg podiatry, vascular surgery)
	- Patients with recurrent wounds, including multiple wounds, are
	eligible; largest ulcer to be index wound - If infection occurs and antibiotics applied, whilst in study, then
	this is not deemed an exclusion criterion.
	 Prophylactic systemic antibiotic use is not an exclusion criterion
	- Chronicity: clinical diagnosis of ulcer with wound duration > 30
	days.
	- Wound type:
	 Leg ulcer (can be venous, mixed or arterial in nature)
	 Foot ulcer (can be diabetic or non-diabetic in nature)
	Exclusion criteria:
	- Aged < 18 years
	- Any reasons for the patient being unable to follow the protocol,
	including lack of mental capacity to consent to taking part in the
	study.
	- The patient has concurrent (medical) conditions that in the
	opinion of the investigator may compromise patient safety or
	study objectives
	- Confirmed and ongoing wound infection at baseline which is
	already being treated with systemic antibiotics (within 3 weeks
	of first study visit) Previous participation in BIOME study
	- Trevious participation in biolivic study
Sample size	258 samples required, taken from minimum of 129 patients at week0
	and week6 visits. This study element is powered to detect a 4%
	difference in detection of clinician-specified wound infection and a
	positive WOUNDCHEK™ Bacterial Status test result. (Chi-squared test,
	80% power, p-value 0.05, 10% attrition rate). This is provided the
	incidence of infection detected equals 9% and 5% per rater,
	respectively.
	Furthermore, the study is also sufficiently powered to detect an inter-
	rater concordance level (Kappa) of 0.9, at 80% power and an infection detection rate of 10%.
	detection rate of 10%.
Manufacturer & provider	WOUNDCHEK™ Laboratories

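### The two kappa adequacy statements disagree, cannot be checked, and do not fit the 5% and 9% rates used to size the study

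*Protocol*

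**What the plan says.** The Sample size row of the Research Protocol Summary first gives the primary scenario, in which the "incidence of infection detected equals 9% and 5% per rater". Its next sentence says the study is also sufficiently powered for an inter-"rater concordance level (Kappa) of 0.9, at 80% power and an infection" detection rate of 10%.

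Section 8.2 repeats the primary scenario in Table 6 (0.05 and 0.09, both labelled hypothetical). It names the raters, "The raters are the WOUNDCHEK WCBC and the clinical staff", and sets the calculation at "80% power and 5% significance, based on two-sided Chi-squared test". The result is "ample size required without any attrition: 234 samples", raised to 258 for 10% attrition. The closing sentence says this size also serves concordance between the same two raters, "at a confidence level of 90% and Kappa concordance level of 0.80", and refers to an online calculator.

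Kappa is a secondary objective (section 2.2) and one of the two analyses listed in section 8.3.

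**The concern.** The two sentences describe one analysis on one set of samples, yet they differ in kappa (0.9 against 0.80) and in kind (80% power against 90% confidence). The figures may have been transposed, but nothing in the text says which version is intended.

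The summary also moves from 5% and 9% to a single 10% between consecutive sentences. Two raters whose positive rates differ by four points must disagree on at least 4% of samples. When positives are rare, that much disagreement takes a large share of the agreement available beyond chance.

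At stake is whether a reader can rely on the statement that the study is large enough for its concordance objective.

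**Working it through.** **Inputs.** Positive rates 5% and 9%, two-sided 5% significance, 80% power, 234 samples before attrition and 258 after (summary; section 8.2 and Table 6). Kappa 0.9 with a 10% rate (summary). Kappa 0.80 with 90% confidence (section 8.2). No null kappa and no target width are given, so the nulls below are assumptions shown over a range.

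**1. The primary figure reproduces.** A chi-squared goodness-of-fit test on 1 df has effect size w = √(0.04²/0.95 + 0.04²/0.05) = 0.1835. The smallest N with 80% power is 234 (power 80.2%). Then 234 × 1.1 = 257.4, rounded up to 258. Both match the protocol.

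**2. Kappa ceiling at 5% and 9%.**
- Chance agreement: 0.05 × 0.09 + 0.95 × 0.91 = 0.0045 + 0.8645 = 0.869.
- Largest possible observed agreement: 0.05 + 0.91 = 0.96.
- Largest kappa: (0.96 − 0.869)/(1 − 0.869) = 0.091/0.131 = 0.695.
- Discordance that each claim allows, (1 − κ) × 0.131: 2.62% for kappa 0.80 and 1.31% for kappa 0.90. The scenario forces at least 4%.

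**3. Using the 10% rate instead.** If both raters are at 10%, the ceiling is 1.0 and kappa 0.9 is attainable, but the difference between raters is then zero. If 10% is read as the average of two rates four points apart (8% and 12%), chance agreement is 0.0096 + 0.8096 = 0.8192 and the ceiling is 0.1408/0.1808 = 0.78, still below both values.

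**4. What the summary's power claim would need.** The goodness-of-fit method for kappa with a common prevalence p = 0.10 uses q = p(1 − p) = 0.09. Cell probabilities are p² + κq (both positive), 2q(1 − κ) (discordant) and (1 − p)² + κq (both negative). N = (1.960 + 0.842)² / Σ[(P₁ − P₀)²/P₀].

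For a null of 0.7 and a true kappa of 0.9, the cells are (0.073, 0.054, 0.873) and (0.091, 0.018, 0.891). The sum is 0.00444 + 0.02400 + 0.00037 = 0.0288, so N = 7.849/0.0288 ≈ 272.4, rounded up to 273.

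| True kappa | Assumed null | Independent samples needed |
|---|---|---|
| 0.9 | 0.6 | 149 |
| 0.9 | 0.7 | 273 |
| 0.9 | 0.8 | 779 |
| 0.80 | 0.5 | 169 |
| 0.80 | 0.6 | 335 |
| 0.80 | 0.7 | 1090 |

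Whether 234 or 258 samples suffice depends on a null that the protocol does not state. Reading the two sentences together, with 0.80 as the null and 0.9 as the expected value, gives 779 and so does not reconcile them with 258.

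**5. Precision that 234 samples give.** With common prevalence, SE = √{(1 − κ)/N × [(1 − κ)(1 − 2κ) + κ(2 − κ)/(2p(1 − p))]}. At κ = 0.4, p = 0.07 (the mean of 5% and 9%) and N = 234, SE = √{0.002564 × [0.12 + 4.916]} = 0.1136, and the 95% half-width is 1.96 × 0.1136 = 0.22. Over kappa 0.2 to 0.69 the half-width is 0.19 to 0.22. The large-sample variance with unequal 5% and 9% margins gives 0.18 to 0.22. These figures assume independent samples. At the other extreme, if the two swabs from each patient carried the same information, 117 patients would count once each and the half-widths would grow by √2, to about 0.26 to 0.31.

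**The case against.** The strongest reply is that 5% and 9% are hypothetical. They form the alternative chosen to power the chi-squared test and are not a forecast. If the raters' rates were equal, the ceiling would be 1.0; at 5% and 7% it would be 0.82. A study may also power two objectives under two scenarios. This stands to the extent that a reader might infer that kappa 0.80 or 0.90 is impossible outright, and the documents do not support that. The ceiling of 0.695 belongs to the 5% and 9% scenario alone. What remains is that the protocol never says it is using two scenarios, and presents both as properties of one sample.

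Three other stronger readings also fail:
- **That the study is too small for kappa.** A true kappa of 0.9 against a null of 0.6 needs only 149 independent samples. The fault is that the claim cannot be checked; a shortfall is not shown.
- **That both sentences are power claims.** Section 8.2 states a confidence level and no power. It may be a precision statement: at kappa 0.80, 10% prevalence and 234 independent samples, the 90% half-width is about 0.11. A power statement and a precision statement can coexist, but these rest on different kappa values and section 8.2 states no target width.
- **That a kappa below 0.69 would count as failure.** The objectives ask only for the degree of concordance. No pass mark for kappa appears anywhere.

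**Conclusion.** The point holds in limited form. The two statements conflict on kappa and on kind, neither can be verified as written, and the 10% rate is inconsistent with the 5% and 9% given for the same raters. If the four-point difference at 5% and 9% is real, kappa is at most 0.695, so neither 0.80 nor 0.90 can also be true. That ceiling is exact arithmetic from the protocol's own rates and is conditional on them. The sample sizes for kappa rest on assumed nulls, a common 10% prevalence and independent samples.

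Severity is low. Kappa is secondary and does not drive the sample size. The harm is an unsupported claim of adequacy for that objective.

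**What to change.** Replace both kappa sentences, in the summary and in section 8.2, with one identical statement tied to Table 6. It should give the 5% and 9% rates, an expected kappa below 0.69, and the 95% interval half-width expected from 234 evaluable samples. For example, with an illustrative expected kappa of 0.5 the half-width is about 0.21 if samples are independent. The statement should add that the interval will be wider because patients contribute up to two swabs, and that it will be calculated at patient level. If a power claim is preferred, state the null kappa, expected kappa, both positive rates, significance level and power, and keep the scenario consistent with Table 6.

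Reporting positive and negative agreement beside kappa is optional; both come from the same 2 × 2 table.

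The cost is a rewrite of two sentences. Recruitment, data collection and the primary calculation do not change.

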8.3 PRIMARY OUTCOME STATISTICS

The WOUNDCHEK™ kit result will be cross tabulated with the clinical staff member's assessment of wound infection. Two tests will explore the relationship in outcomes between clinical judgement and WOUNDCHEK™ kit detection testing:

- Chi-squared test (cross-tabulation of results); primary outcome measure
- Kappa inter-rater concordance level.

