Prospective, single-centre, cohort study assessing the potential application of WOUNDCHEK™ diagnostics for ulcer management

(BIOME, Bacterial Infection: Observation & Management Evaluation)

V1, dd 18 November 2022

Chief Investigator's Statement of Ownership and Content.
I, [name], confirm that this protocol is my work and is owned by me. The protocol conforms to standards outlined in the Declaration of Helsinki 1964.
Name (PRINT):
Signature:
Date:

RESEARCH PROTOCOL SUMMARY

TITLE:	Prospective, single-centre, cohort study assessing the potential application of WOUNDCHEK™ diagnostics for ulcer management
Short title:	BIOME, Bacterial Infection: Observation & Management
	Evaluation
IRAS number	314595
Device description	CE-marked point of care test: WOUNDCHEK™.
	WOUNDCHEK™ Bacterial Status — or WCBS - is able to detect bacterial EPA (elevated protease activity). WOUNDCHEK™ Bacterial Status will help clinicians establish within minutes which wounds may most benefit from a protease modulating therapy, ensuring appropriate and targeted use of these therapies.
Study design	Prospective, single-centre, controlled, non-randomised, prospective cohort comparative study
	Participants' index ulcer will be swabbed twice, at week 0 and at week 6, plus a medium-term assessment at week 12.
Primary objective	Determine if there is a difference in rate of positive outcome between clinical opinion (ie presence of infection based on wound symptoms) and WOUNDCHEK™ Bacterial Status test result for the same wound.
Secondary objectives	To define the degree of concordance between a clinical staff member's opinion and results from the WOUNDCHEK™ detection kit, concerning the assessment of infection presence in ulcer wounds.
	Determine what patient and/or wound characteristic(s) are significantly linked to a non-matching result between clinical opinion and WOUNDCHEK™ WCBS result. These outcomes are relevant for application of the WOUNDCHEK™ test in standard clinical practice. Two binary logistic regression analyses will be conducted for variables associated with the sample's proportion of non-matched outcome: - Clinical opinion negative ('no infection') vs WOUNDCHEK™ test positive or - Clinical opinion positive ('possible' or 'definite' infection) vs WOUNDCHEK™ test negative

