2 OBJECTIVES

2.1 PRIMARY OBJECTIVE

Determine what patient and/or wound characteristic(s) are significantly linked to a non-matching result between clinical opinion and WOUNDCHEK™ Bacterial Status (WCBS) result. These outcomes will be relevant for application of WOUNDCHEK™ test in standard clinical practice. See Table 2.

Table 2. Outcome options for WOUNDCHEK $^{\text{\tiny M}}$ and clinical inspection, with the two non-matching outcome options shaded in green and blue respectively.

	WOUNDCHEK™	WOUNDCHEK™
	Bacterial Status	Bacterial Status
Clinical opinion:	negative	Positive
no infection		
Clinical opinion:	negative	Positive
possible infection		
Clinical opinion:	negative	Positive
infection		

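### The primary chi-squared test on the kit-by-clinician cross-tabulation tests association, not a difference in positive rates, so it cannot answer the Summary's primary objective

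*Protocol*

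**What the plan says.** The primary objective in the protocol Summary is "Determine if there is a difference in rate of positive outcome between clinical opinion" and the "Bacterial Status test result for the same wound". The Summary and section 8.2 size the study for a 4-point difference, 9% against 5%, at 80% power and two-sided 5% significance. They arrive at 234 samples, or 258 with attrition.

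Section 8.3 says that the "kit result will be cross tabulated with the clinical staff member's assessment of wound infection". It continues: "Two tests will explore the relationship in outcomes between clinical judgement and" kit testing. The first of the two is "Chi-squared test (cross-tabulation of results); primary outcome measure"; the second is kappa. No paired test of the two rates is named anywhere in the protocol.

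Two other passages bear on this:

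- Section 2.1 gives a different primary objective, namely which "characteristic(s) are significantly linked to a non-matching result between clinical opinion and" the kit result.
- Table 2 in section 2.1 has three clinical categories (no, possible, definite infection). Possible and definite are combined into one positive category only where the logistic regressions are described, in the Summary and in section 8.4.

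**The concern.** Each wound yields two binary results, one from the clinician and one from the kit. Whether the two positive rates differ depends only on the discordant wounds: those positive by one method and negative by the other. Pearson's chi-squared on the kit-by-opinion table asks something else, namely whether knowing one result helps to predict the other.

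The two questions can have opposite answers. Methods that agree well and have identical rates give a very small p-value. Methods that are unrelated but find infection at quite different rates give a large one. A reader who takes the primary p-value as the answer to the Summary's objective would be misled in both cases.

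Both cases are plausible here. The kappa planning values of 0.9 (Summary) and 0.80 (section 8.2) presume strong agreement. The Background reports that earlier work with this kit found no strong association between clinical signs of infection and a positive test.

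**Working it through.** **Inputs from the protocol.** Positive rates 9% and 5%; difference d = 0.04; alpha 0.05 two-sided; power 80%; effect size 0.184; 234 samples before attrition and 258 after (Summary, section 8.2, Table 6). The overlap between the two methods that goes with these rates is not given, so every kappa and discordance below is an assumption and is shown over a range.

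**1. The plan's own figure.** Take 5% as a fixed, known null and 9% as the alternative in a one-sample goodness-of-fit chi-squared with 1 df:

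- w = √(0.04²/0.95 + 0.04²/0.05) = √0.03368 = 0.1835
- The smallest N with 80% power at non-centrality N·w² is 234 (power 0.802)
- 234 × 1.10 = 257.4, rounded up to 258

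The figure reproduces, but only for a test of one rate against a constant. That is neither the cross-tabulation test of section 8.3 nor a paired comparison. Two independent groups at 5% and 9% would need 638 per group. Goodness of fit with 9% as the null would need 402.

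**2. Two tables with 234 wounds.** Rows are one method (negative, positive) and columns the other. Association χ² = n(ad − bc)² / (product of the four margins). McNemar χ² = (b − c)² / (b + c).

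| Table | Positive rates | Association χ² | McNemar χ² |
|---|---|---|---|
| [217, 5; 5, 7] | 12/234 and 12/234 (equal) | 234(1519 − 25)² / (222·12·222·12) = 73.6, p ≈ 10⁻¹⁷ | 0, p = 1.0 |
| [180, 10; 42, 2] | 44/234 (18.8%) and 12/234 (5.1%) | 234(360 − 420)² / (190·44·222·12) = 0.04, p = 0.85 | 32²/52 = 19.7, p ≈ 9×10⁻⁶ |

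The planned test is overwhelmingly significant where the rates are identical, and null where they differ by nearly 14 points.

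**3. Rejection rates at n = 258.** These come from 40,000 simulated tables per scenario, with samples treated as independent and no continuity correction. Cells were built from the marginal rates and kappa: Pe = p₁p₂ + (1 − p₁)(1 − p₂), Po = κ(1 − Pe) + Pe, p₁₁ = (Po − 1 + p₁ + p₂)/2.

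| True rates | Assumed kappa | Section 8.3 chi-squared | McNemar |
|---|---|---|---|
| 9% and 9% | 0.3 | 96% | 5% |
| 9% and 9% | 0.6 | about 100% | 5% |
| 9% and 5% | 0 (unrelated) | 4% | 43% |
| 9% and 5% | 0.1 | 41% | 48% |
| 9% and 5% | 0.3 | 96% | 59% |

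As a check, χ² ≈ n·φ², and φ = κ when the margins are equal, so kappa 0.6 gives 258 × 0.36 = 93, far beyond the 5% critical value of 3.84. The chi-squared column changes with kappa. With kappa at 0.3 it is 96% whether or not the rates differ.

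**4. What a paired test would need.** McNemar: N = [1.96√p_d + 0.8416√(p_d − d²)]² / d², with p_d the discordant proportion. With rates of 9% and 5%, p_d can lie only between 4% (every wound positive by the lower-rate method is also positive by the other) and 14% (no overlap).

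| p_d | Pairs for 80% power, before attrition | Power at 234 pairs |
|---|---|---|
| 4% | 194 | 0.87 |
| 6% | 292 | 0.71 |
| 8% | 391 | 0.58 |
| 10% | 489 | 0.49 |
| 13.1% (unrelated) | 641 | 0.39 |
| 14% | 685 | 0.37 |

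**The case against.** **Another layout may have been meant.** Table 6 sets out rater by result, and a chi-squared on that layout would compare rates. Its only fault would be to ignore the pairing, which at equal 9% rates and kappa 0.3 makes it conservative (about 2% rejection at n = 258), not grossly anti-conservative. But section 8.3 describes the kit result cross-tabulated with the clinical assessment, which is the association table. The rater-by-result reading would also need 638 per group and would not rescue the 234. What stands is that sections 8.2 and 8.3 do not describe the same test.

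**The Summary's objective is not the only one.** Section 2.1 states a different primary objective, so the point must be limited to the Summary's version. That narrows it without removing it. The chi-squared does not answer the section 2.1 objective either; the regressions in section 8.4 do.

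**The scenarios are chosen.** The kappas are assumptions, and the 4% rejection rate at 9% against 5% holds only at exact independence; it is already 41% at kappa 0.1. This is fair. The general statement is that rejection follows overlap, not that power is always at alpha.

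**The three-category table is a detail for the SAP.** The Summary does define positive clinical opinion as possible or definite, and Table 2's caption implies two kinds of mismatch. Both, however, concern the non-matching analyses, so the primary table is still not explicitly dichotomised. This part is secondary.

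**The protocol claims only to explore a relationship.** It does use that word, but it also labels the chi-squared as primary and sizes the study for a difference in rates.

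**Conclusion.** The concern holds. This is a wrongly specified primary test, not a detail left for the SAP, and it must be corrected before analysis. That an independence test does not address equality of paired rates rests on no assumption. The size does: with equal rates of 9%, a significant result would occur in 96% to about 100% of studies at kappa 0.3 to 0.6. With the planned 9% and 5%, rejection runs from 4% (unrelated results) to 96% (kappa 0.3) at n = 258. These figures treat all samples as independent, although two come from each patient.

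A correct paired test may be underpowered at the planned size: power at 234 pairs is 0.87 to 0.37 over the possible discordance. This is no reason to keep the present test, because the calculation in section 8.2 does not support it either.

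**What to change.** - **Section 8.3 and the Summary:** make the primary analysis the difference between the two positive rates on the same wounds, with its 95% confidence interval and McNemar's test. Because week 0 and week 6 samples from one patient are pooled, use a form that allows for clustering, for example GEE with method (clinician or kit) as the factor and patient as the cluster. Keep the cross-tabulation and kappa as description.
- **Dichotomy:** state in section 8.3 that possible and definite infection count as positive for the primary comparison, as section 8.4 already does for the regressions.
- **Objective:** reconcile the primary objective in the Summary with that in section 2.1, so that the primary test has one question to answer.
- **Section 8.2:** replace the goodness-of-fit calculation by one for the paired test, with a stated and justified discordance, and say whether 258 samples still suffice.

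The changes to the test and dichotomy are a few sentences, need no new kind of data and can be run in SPSS. The real cost lies in section 8.2: depending on the discordance assumed, either the number of samples or the claimed power may have to change.
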